## PROTOCOL SYNOPSIS

[figure not shown]
Title:	A Placebo-Controlled Randomized Withdrawal Evaluation of the Efficacy and Safety of
	Baclofen ER Capsules (GRS) in Subjects with Spasticity Due to Multiple Sclerosis
Study Design:	This 21-week study will be performed in three parts:
	: Open-label, run-in
	(Part 1)  Open-label part in which subjects are converted to the corresponding dose of
	(Part 2)
	: Double-blind
	(Part 3)
	)
	A
	Subjects will be encouraged to come for one additional unscheduled visit during this interval in order to
	for one additional discheduled visit during this interval in order to
	The schedule of assessments is provided in Table 1.
Objectives:	Primary Objectives:
	The primary objectives are to compare the continued treatment with
	
 
Demonstrating efficacy
 
Indirectly demonstrating
 

	Indirectly demonstrating
	Determining the safety
	Secondary Objectives:
	To determine effects on other corollary measures of spasticity such as:
	
 
Subject's assessment of spasticity severity
 

	Exploratory Objectives:
	The following will be explored:
	•
	•
	Effect of concomitant medication use and disease characteristics on
	• Effect of concomitant medication use and disease characteristics on
Data Fee	
Primary Efficacy Outcome:	The primary efficacy outcome is the proportion of subjects who become a treatment failure during double-blind randomized withdrawal (Part 3). Each subject's response will be
Suttome.	determined after database lock, but prior to unblinding the data. A subject who meets the
	following criterion will be considered a treatment failure:
	A CGIC of > 5 ("minimally warsa" to "yarr much") and at least and
	
 
A CGIC of ≥ 5 ("minimally worse" to "very much worse") and at least one movement with a ≥ 1 unit increase  in modified Ashworth score from baseline
 

 $^{\rm 1}$  A change from 1 to 1+ and 1+ to 2 will be counted as a 1-unit change

Confidential Page 2 of 67

	The modified Ashworth score will be assessed at each clinic visit, recorded for each of the 12
	movements evaluated. The Baseline score against which worsening will be determined
	For the primary efficacy analysis, subjects who provide modified Ashworth and CGIC scores at Visit 11 and meet the treatment failure criterion at Visit 11, or who have met the treatment failure criterion at any prior visit will be classified as being treatment failures. All other subjects will be classified as not being treatment failures.
Secondary Efficacy Outcomes:	Subject Global Impression of Severity (SGIS)
Safety Assessments:	
 
Treatment Emergent Adverse Events
 
Daytime sedation
 
Vital Signs (seated blood pressure and pulse)
 
Clinical laboratory tests
 
12 Lead ECG
 
Physical examination and neurological evaluation
 
Columbia – Suicide Severity Rating Scale
 

Treatments:	•
Study Population:	Subjects aged 18 years and above with spasticity due to multiple sclerosis with acceptable symptom control
Number of Subjects:	Approximately 300 subjects will be enrolled to ensure that at least 240 subjects are randomized at the beginning of
Number of Centers:	Up to 35 centers
Setting:	Out-patient clinics
Statistical Methods:	Efficacy Analyses: The primary efficacy analysis will be performed on an intent-to-treat (ITT) population, defined as all subjects who were randomized to double-blind study drug at Visit 7 and subsequently received at least one dose of study medication.
	).
	A per protocol (PP) population may also be analyzed (if it differs from the ITT population overall by more than 10% in sample size), defined as all ITT population subjects who had at least one on-treatment assessment in Part 3, and did not have any major protocol violation (such as poor compliance).

Confidential Page 3 of 67

Confidential Page 4 of 67

used medications.

Subject listings will be provided for all safety parameters as well as recently and concurrently

Table 1: STUDY DESIGN AND SCHEDULE OF ASSESSMENTS

		1 a	DIC 1. 510	DESIGN I	ALID SCHED	ULE OF ASS	ESSIVIE VIS					
Visit	S	Run- In		Open-La	abel				Double-		bo-Controlle ation	d Down-
	Screening											
	(-14 days)	Visit 1	Visit 2	Visit 3	Visit 4	Visit 5	Visit 6	Visit 7	Visit 8	Visit 9	Visit 10	Visit 11
Week												
Informed consent	×		_			_						
Demographics	×											
Medical and medication	×	×										
history												
Physical examination 	×											× 
Neurological examination	×											× 
Vital sign measurements 	×	×	×	×	×	×	×	×	×	×	×	×
		x										
Clinical laboratory testing 	×							×			1	× 
Urine pregnancy test 	×							×				× 
ECG	×11		× 		x 			×12				×2, 12
Dispense Medication		×	×	×	×	×	×	×				
		×										
			×	×								
					×	×	×					
Randomization								×				
								×	×	×	×	
Modified Ashworth Score	×	×	×	×	×	×	×	×	×	×	×	×
Clinician Global Impression of Change (CGIC)					×			×	×	×	×	×
Subject Global Impression of Severity (SGIS)					×			×	×	×	×	×
Adverse events assessment	×	×	×	×	×	×	×	×	×	×	×	×
C-SSRS Assessment	×	×	×	×	×	×	×	×	×	×	×	×
Dispense and Collect Diary		׳	×	×	×	×	×	×	×	×	×	× 
Check compliance			×	×	×	×	×	×	×	×	×	×
Concomitant medications	×	×	×	×	×	×	×	×	×	×	×	×
Pharmacokinetic blood	×				×2	×2	×3	×3				
sampling												

<sup>2 Tests and measurements to be performed if needed  Dispense diary only  Collect diary only

Confidential Page 5 of 67

 Resting pulse and blood pressure measurement (sitting)

Urinalysis: Dipstick for pH, specific gravity, Microscopic examination of the sediment

Confidential Page 6 of 67

<sup>5 Subjects will be encouraged to come for one additional unscheduled visit between

<sup>6 The complete examination will consist of evaluation of the skin, head, eyes, ears, nose, throat, neck, thyroid, lungs, heart, lymph nodes, abdomen, and extremities

<sup>7 The examination is to consist of an evaluation of mental status; corneal reflexes; extra-ocular movements; facial sensation (light touch); facial strength; palatal movement; tongue movements; neck extension; neck flexion; head turning; respiration; forced vital capacity; tendon reflexes of the right and left biceps, triceps, supinator, quadriceps, and ankle (scored as 0=absent, 1=reduced, 2=normal, 3=increased, 4=clonus); and plantar stimulation (scored as 0=no movement or flexor; 1=extensor).

<sup>10 Urine pregnancy test (for women)

<sup>11 Done only one time

<sup>12 Done in triplicates at two minutes intervals

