#### 10.3 Study Populations

#### 10.3.1 Efficacy Populations

#### 10.3.1.1 ITT Population

The ITT population will be defined as all subjects who are randomized to double-blind study drug at Visit 7 and subsequently received at least one dose of study medication.

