#### 10.4.3 Efficacy Analysis

#### 10.4.3.1 Primary Efficacy Analysis

The primary efficacy analysis will be performed using the intent-to-treat (ITT) population.

A subject will be classified as ,treatment failure" if the definition for failure (Section 10.1) is met at any time during the double-blind withdrawal period (Part 3).

The primary efficacy analysis will be carried out using a two-sided test at the alpha=0.05 level of

[figure not shown]
primary efficacy analysis will be carried out using a two-sided test at the alpha=0.05 level of significance.

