#### 2. INTRODUCTION

This Statistical Analysis Plan (SAP) describes the planned statistical analyses to be performed for the analysis of data from Study CLR\_09\_21, "A Placebo-Controlled Randomized Withdrawal Evaluation of the Efficacy and Safety of

in Subjects with Spasticity Due to Multiple Sclerosis."

The SAP is prepared to provide a more technical and detailed elaboration of the principal statistical features stated in the protocol. The SAP will ensure that the tables, listings, and figures that will be produced and statistical methods that will be used are complete and accurate and will allow valid conclusions to be drawn. In the development of this SAP, the following documents were used:

- Protocol Number Version 7.0 Amendent 04, 16 Dec 2016
- Electronic Case Report Form (eCRF), 09 Mar 2012

The principles in the following guidance documents are followed in preparation of this SAP:

- International Conference on Harmonisation (ICH) E3 (1995): Structure and Content of Clinical Study Reports
- ICH E6 (1996): Guideline for Good Clinical Practice
- ICH E9 (1998): Statistical Principles for Clinical Trials

In the event that a discrepancy is found between the descriptions in the statistical section of the protocol and this document, the description in this document supersedes the descriptions in the statistical section of the protocol.

The responsible party at SPARC Ltd. will be required to review and approve all versions of the SAP.

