#### **Intent-to-Treat (ITT) Population:**

The ITT population will be defined as all subjects who are randomized to double-blind study drug at Visit 7 and subsequently received at least one dose of study medication, and have one subsequent modified Ashworth and CGIC score at the same assement.

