### 6.1 Study Subjects

### 6.1.1 Subject Disposition

The final study disposition of each subject will be captured in the eCRF. For those subjects who do not complete the study as planned, all potential reasons for discontinuation should be provided, with one indicated as primary. The reasons for discontinuation will be categorized as described below and the following descriptive summaries of study disposition will be provided.

- Number of subjects who were enrolled in each phase of the study (Part 1, Part 2, Part 3):
  - o Part 1: Received at Visit 1
  - o Part 2: Received at Visit 2 (Safety Population)
  - o Part 3:
    - Randomized at Visit 7
    - Dispensed Blinded Study Drug at Visit 7 (Safety Population Part 3) by treatment group and overall
    - Intent-to-Treat Population by treatment group and overall
    - Per Protocol Population by treatment group and overall
- Number and proportion of subjects (overall for Parts 1 and 2 and by treatment group and overall for Part 3) who discontinued each phase of the study.
- Number and proportion of subjects (overall for Parts 1 and 2 and by treatment group and overall for Part3) who dropped-out for each of the following categories (based on primary reason and also based on all reasons) for why a subject may be prematurely discontinued from the study.

- Withdrew Consent
- Adverse Event
- MS-related Disease Progression

0

- Required Dose Change Between Visit 4 and Visit 11
- Major Protocol Deviation
- Lost to Follow-up
- Worsening of Clinical Condition or Loss of Efficacy
- o Withdrew, Per Sponsor
- o Withdrew, Per Investigator
- Other

A listing of subject disposition will be prepared, inclusive of dates of last dose and last contact, and any investigator comments regarding reason for discontinuation. A summary table will tabulate overall disposition of the subjects by the categories above. A CONSORT figure will summarize subject disposition.

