#### 6.2.1.3 Derivation of Primary Endpoint

The primary efficacy variable is the proportion of subjects who become a Treatment Failure during the double-blind randomized withdrawal part (Part 3). Using the primary efficacy variable, the CRO will perform a determination of failures (the blinded failure analysis). A subject's response status will be determined after database lock, but prior to unblinding the data. A subject who meets the following criterion will be considered a treatment failure:

• A CGIC of ≥ 5 ("minimally worse" to "very much worse") and at least one movement with a ≥ 1 unit increase in MAS from Baseline (A change from 1 to 1+ and 1+ to 2 will be counted as a 1-unit change)

The MAS at a given visit will be	e recorded for each of the	12 movements measured.	

For the Treatment Failure analysis, subjects who provide MAS and CGIC scores at Visit 11 and meet the treatment failure criterion at Visit 11,

21Sep2017

All other subjects will be classified as not being Treatment Failures.

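### On the readable text, leaving Part 3 for worsening does not count as failure, and the SAP's ITT set drops such subjects if they have no joint rating

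*Protocol*

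**What the plan says.** The protocol synopsis, under the primary efficacy outcome, counts a subject as a failure if the joint criterion (CGIC of 5 or more plus a rise of at least one unit in at least one of the 12 Ashworth movements) is met at Visit 11 or at any earlier visit. It closes with "All other subjects will be classified as not being treatment failures". Protocol 10.4.3.1 likewise counts a failure at any time in Part 3. SAP 6.2.1.3 repeats the criterion and ends with "All other subjects will be classified as not being Treatment Failures", but the text just before that sentence is not readable.

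The two ITT definitions differ. Protocol 10.3.1.1 takes all subjects "randomized to double-blind study drug at Visit 7 and subsequently received at least one dose of study medication". SAP 5.1 adds that they must "have one subsequent modified Ashworth and CGIC score at the same assement". SAP section 2 settles which applies: where the two disagree, "the description in this document supersedes the descriptions in the statistical section of the protocol".

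SAP 6.1.1 lists "Worsening of Clinical Condition or Loss of Efficacy" as a discontinuation category and asks that "all potential reasons for discontinuation should be provided, with one indicated as primary". SAP 6.2.1.6 plans sensitivity analyses under other assumptions about the response status of subjects with missing data, within the ITT population. Their details are not readable.

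**The concern.** In a randomized-withdrawal trial, loss of control after the drug is withdrawn is the event being counted. A subject who leaves Part 3 because spasticity has worsened is a plausible case of that event. The readable primary rule gives the reason for leaving no role, so this subject counts only if both ratings were taken and both qualified. Otherwise the subject is scored in the favourable category or, if never jointly rated, left out.

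The SAP's ITT set also conditions on data collected after randomization, while the protocol's does not. If treatment affects who leaves before a joint rating, the SAP set no longer compares the groups as randomized. If hidden exits fall mainly on placebo, the treatment difference shrinks. If they fall mainly on active, it is inflated in the drug's favour. If they are balanced, little changes.

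**Working it through.** **Applying the rules.** Take a subject randomized and dosed at Visit 7 who leaves Part 3 for worsening.

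- (a) Joint criterion recorded at any Part 3 visit, including an exit visit: failure in both documents.
- (b) At least one joint rating, none qualifying: in the SAP ITT and scored a non-failure. The 6.2.1.6 analyses may re-score this subject.
- (c) No joint rating after Visit 7: in the protocol ITT as a non-failure, but outside the SAP ITT. The 6.2.1.6 analyses run on the ITT set and cannot reach this subject. Nor can the time-to-dropout table, which SAP 9.1 also plans on the ITT set.

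Cases (b) and (c) are the point.

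**Inputs for scale.** The documents give at least 240 randomized and a two-sided 0.05 test (SAP 3.2.1 and 6.2.1.5). No power, failure rates or allocation ratio are readable, so there is no stated power to reproduce. Assumed: 1:1 allocation (240 / 2 = 120 per arm) and true failure rates of 30% active and 50% placebo, including the hidden failures. Let h be the hidden fraction in an arm.

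**Power.** Power = Φ((|p2 − p1| − 1.96·s0) / s1), where s0 = √(p̄(1 − p̄)(1/n1 + 1/n2)) and s1 = √(p1(1 − p1)/n1 + p2(1 − p2)/n2).

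- Base: p̄ = 0.40, s0 = 0.0632, s1 = 0.0619; (0.20 − 1.96 × 0.0632) / 0.0619 = 1.228; power 0.89.
- Hidden failures scored as non-failures: the rate becomes p − h and n stays 120. With 2% active and 5% placebo: 0.28 vs 0.45, s0 = 0.0622, s1 = 0.0612; (0.17 − 1.96 × 0.0622) / 0.0612 = 0.788; power 0.78.
- Hidden failures excluded: the rate becomes (p − h)/(1 − h) and n becomes 120(1 − h). Same case: 0.28/0.98 = 0.286 on 117.6 and 0.45/0.95 = 0.474 on 114; power 0.84.

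| Hidden, active / placebo | Scored: difference, power | Excluded: difference, power |
|---|---|---|
| 0.5% / 2% | 18.5 points, 0.84 | 19.3 points, 0.87 |
| 1% / 3% | 18.0 points, 0.82 | 19.2 points, 0.86 |
| 2% / 5% | 17.0 points, 0.78 | 18.8 points, 0.84 |
| 3% / 10% | 13.0 points, 0.57 | 16.6 points, 0.74 |
| 2% / 2% | 20.0 points, 0.90 | 20.4 points, 0.90 |
| 3% / 1% | 22.0 points, 0.94 | 21.7 points, 0.93 |

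The 3% / 10% row means about 12 of 120 placebo subjects with a hidden failure and is an extreme. In the last row power rises because the difference is inflated. If treatment affects neither failure nor concealment (35% in both arms, 2% hidden in each), the rejection rate stays at 0.05.

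**Counts** (chi-square without continuity correction). At the assumed rates the true table is 36/120 vs 60/120, p = 0.0016.

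- Scored as non-failures: 9 hidden on placebo and none on active gives 36/120 vs 51/120, p = 0.044. With 10 vs 0 it is 36/120 vs 50/120, p = 0.059.
- Excluded: 12 vs 0 gives 36/120 vs 48/108, p = 0.024, still significant.

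The margin depends on the starting table. From a weaker 36/120 vs 54/120 (p = 0.016), 4 vs 0 scored (36/120 vs 50/120, p = 0.059) or 6 vs 0 excluded (36/120 vs 48/114, p = 0.054) is enough.

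**The case against.** The strongest objection is that the design leaves few such subjects. Protocol 5.3 requires withdrawing subjects to have the final-visit procedures, and the final-visit list in Protocol 4.4.4.5 includes both ratings. Protocol 4.1 has subjects seen weekly in Part 3, or sooner if needed. The bar for failure is low, so most rated subjects leaving for worsening would qualify. The placebo arm is down-titrated (SAP 6.1.8), which makes loss of control before Visit 8 less likely. This stands as an argument about size. It does not close the gap, because Protocol 7.1.1 asks for exit examinations only as far as possible.

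Second, a counter-rule may sit in text that cannot be read: Protocol 10.1, parts of 10.4.3.1 and 10.4.3.2.1, and parts of SAP 6.2.1.3 and 6.2.1.5. A reader might infer that the plan has no rule at all for such exits. The documents do not support that; only the readable text can be judged. The synopsis classification and both ITT definitions are readable, though, and the conflict between the definitions does not depend on the hidden text.

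Third, a reader might infer that the excluded subjects vanish from the report. They do not. They remain in the disposition outputs, the Part 3 safety tables and the All Enrolled listings, which include treatment failure and Ashworth listings (SAP 9.1). They are missing from the ITT efficacy comparison and its response-status sensitivity analyses.

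Fourth, making worsening exits part of the primary endpoint would add an investigator-recorded reason that is not specific to spasticity to an endpoint built on ratings. That is a fair objection, and the fix avoids it.

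**Conclusion.** The point holds on the readable text as a cheap improvement, not a fatal flaw. Two things are established: the readable primary rule ignores the reason for exit, and the SAP's ITT set drops randomized and dosed subjects whom the protocol's set keeps, beyond the reach of the planned response-status sensitivity analyses.

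The size is uncertain and probably small. Every rate used is assumed, as is 1:1 allocation. With hidden failures between 0.5% / 2% and 2% / 5% (active / placebo), power falls from 0.89 to between 0.84 and 0.78 if they are scored as non-failures, and to between 0.87 and 0.84 if excluded.

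Two stronger readings are tempting. One is that a handful of subjects would decide the trial. At the assumed 30% vs 50% it takes an imbalance of 10 vs 0 scored as non-failures to lose significance; the 4 vs 0 figure arises only from a result already nearer the boundary. The other is that the rule works against the drug. The documents give no exit rates by arm, so the direction is open.

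**What to change.** Two SAP changes.

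1. In 5.1, define the ITT population as all subjects randomized at Visit 7 who received at least one dose, as in Protocol 10.3.1.1, and state that the 6.2.1.6 sensitivity analyses use this set. Keep the present SAP set, which requires a joint rating, as a supportive analysis.
2. In 6.2.1.6, add a pre-specified sensitivity analysis on this set that counts Part 3 discontinuation for worsening or loss of efficacy as treatment failure, whether it is the primary or any recorded reason, with relation to spasticity confirmed in the blinded review (5.5). Report these exits by arm.

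The primary endpoint definition stays as it is. No new data or protocol amendment is needed: reasons for discontinuation are already collected, the blinded review already covers populations and missing data, and the first change brings the SAP back to the protocol.

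The cost is a SAP revision, a little more analysis work and one trade-off. Never-rated subjects, whatever their reason for leaving, enter the primary analysis as non-failures under the existing default. That can cost a little power: at most the gap between the two power columns above for true failures among them. The second change shows how much of this comes from recorded worsening.

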#### LIST OF ABBREVIATIONS

ADR Expanded Form
Adverse Drug Reaction

AE Adverse Event

ALT (SGPT) Alanine aminotransferase (Serum Glutamate Pyruvic Transaminase)

ANCOVA Analysis of Covariance

AST (SGOT) Aspartate aminotransferase (Serum Glutamate Oxaloacetate Transaminase)

BUN Blood Urea Nitrogen °C Degree (Celsius)

C-CASA Columbia Classification Algorithm of Suicide Assessment

CI Confidence Interval
CNS Central Nervous System

CRF Case Record Form/ Case Report Form

CRO Contact Research Organization

C-SSRS Columbia – Suicide Severity Rating Scale

DCF Data Clarification Form

DCGI Drugs Controller General of India

EC Ethics Committee
ECG Electro-Cardiogram

e.g. For example

GABA Gamma- Amino-Butyric Acid
GCP Good Clinical Practice

GGT Gamma Glutamyl Transpeptidase

GLUC Glucose

GMP Good Manufacturing Practice
GRS Gastro-Retentive System

Hb Hemoglobin

HDPE High Density Poly-Ethylene
HIV Human Immunodeficiency Virus

IB Investigator's Brochure

ICH International Conference on Harmonization

IEC Independent Ethics Committee
IP Investigational Product

IRB Institutional Review Board

ITT IUD Intention-To-Treat Intra-Uterine Device

IVRSInteractive Voice Response SystemIWRSInteractive Web Response SystemLOCFLast Observation Carried ForwardMAOIMonoamine Oxidase Inhibitor

mg Milligram
min Minute
mL Milliliter

MS Multiple Sclerosis

nSAE Non-Serious Adverse Event
OD Once Daily (every 24 hours)

SGIS Subject Global Impression of Severity

PI Principal Investigator

PP Per Protocol
QC Quality Check

Confidential Page 10 of 67

R&D Research and Development
SAE Serious Adverse Event
SAP Statistical Analysis Plan
SOPs Standard Operating Procedures

SPARC Ltd. Sun Pharma Advanced Research Company Limited SUSAR Suspected Unexpected Serious Adverse Reaction

TEAE Treatment Emergent Adverse Event

UTI
ULN
Upper Limit of Normal
VAS
Visual Analogue Scale
WBC
White Blood Cell

Confidential Page 11 of 67

## 2 BACKGROUND INFORMATION

## 2.1 Investigational Product

[figure not shown]
## 2.1.1 Name and Description

Confidential Page 14 of 67

have be	een used intercha	Tl ngeably throughout	ne terms study the document to	drug, study n o denote inves	nedication, study tigational produ	y treatmen ct.
2.1.2	Clinical Data to	Date for				

[figure not shown]
Confidential Page 15 of 67

Confidential Page 16 of 67

2.2	Summary of the Known and Potential Risks and Benefits, If Any, to Human Subjects
The	nost common adverse effects are
THE 1	most common adverse effects are
	Description of the Justification for the Route of Administration, Dosage, Dosage Regimen, and Treatment Period(s)

Confidential Page 17 of 67

